**Table 3. Assessment of implementation factors guided by CFIR (Specific Aim 2).**

CFIR Domain	Construct measured	Measured by	Timepoint(s)
Intervention characteristics	Attitudes about FLOW	Qualitative interviews	Baseline; Implementation
Outer setting	Facility resources	Facility complexity	Baseline
Inner setting	Readiness to change	Organizational Readiness for Implementing Care	Baseline
	Facility staffing	Staff to patient ratio in SMH; PCMH penetration rate; PCP mean panel size; Turnover in staffing	All phases
	Facility organization	Degree with which PCMH is integrated in PC; Existence of active Behavioral Health Interdisciplinary Program teams	All phases
	Facility climate	VA Clinical Practice Organizational Survey Provider qualitative interviews	Baseline; Implem. phase
	Inter-service clarity of roles	Existence of MOU between SMH and PC outlining roles and how patient care responsibilities are divided	All phases
Characteristics of the individuals	Provider support for change	Provider qualitative interviews	Implem. phase
	Leadership support	Provider survey and qualitative interview data regarding leadership support	Baseline; Implem. phase
Process	Facilitator behaviors	% of FLOW meetings attended; IF's documentation of their activities; Actual protected time; Provider interview questions re: IF behaviors; Qualitative interviews of Ifs	Implementation phase

**Implementation phase data collection.** The majority of data during the implementation phase will be collected via VA administrative databases. Use of the FLOW EMR template, extracted from administrative databases, will provide information on reach (% of patients transitioned pre vs. post FLOW implementation), effectiveness (% of patients who receive follow up MH care in PC, based upon filled prescriptions, and % of MH patients who return to SMH, based upon consult and appointment data), and adoption (% of providers using the template at least three times, average rates of transition by provider). We will also track demographic characteristics of transitioned patients to examine whether transition rates differ by gender and ethnic/racial background. CDW clinical/administrative data will also be used to collect information on the impact of FLOW on access by tracking the percentage of all SMH clinic patients who receive an appointment within 0 to 7 days of the preferred date. A second measure of effectiveness will be the expected gain in provider time for new patient appointments as a consequence of transitioned patients. This will be calculated for each provider as # of patients discharged multiplied by the average yearly minutes spent in appointments with a patient. We will also examine impact on provider time available for new patients by tracking the number of completed new patient appointments by provider from pre-post implementation of FLOW.

Brief qualitative interviews will assess the satisfaction of Veterans and providers (see interview guides in Appendix). Veterans will be recruited via 'opt out' letter sent to those who transitioned, stratified by site. Final n will be determined by saturation, but we propose 45 Veterans across the seven sites. Veteran qualitative interviews assess satisfaction, perception of appropriateness of the transition and the transition process, and satisfaction with care post-transition. Veterans will complete the interview via phone and receive compensation of \$30. Provider qualitative interviews will assess perceptions of clinical appropriateness, effectiveness, implementation barriers and facilitators such as leadership support and local champion actions that facilitated implementation (see Appendix for draft interview guide). Providers will be recruited by email and will not be compensated. We will interview at least 3 providers at each site (n = 27) to enable understanding of differences across sites. All interviews will be audio recorded, transcribed by a professional transcription service (see revised budget), and coded by two experienced qualitative coders using rapid qualitative analysis.

To assess implementation, the FLOW implementation team, in collaboration with the local champion, will continuously update, at least once per month, each site's FLOW checklist to monitor which aspects of FLOW

are being implemented with fidelity. Local champions will also be asked to document their time spent in various activities (for example, logistical support vs. influencing providers) in order to understand the key ingredients of facilitation in the local context. We will also examine the number of FLOW meetings the local champion attended (% of scheduled meetings) and their actual protected time, to understand whether the champion's availability and time influence implementation.

**Maintenance phase data collection.** After a 1-year implementation phase, the FLOW team will phase out external facilitation and the facility will be encouraged to continue using FLOW locally. Maintenance phase data will continue to be collected on all reach, effectiveness, adoption, and implementation outcomes.

**Power analysis.** Power calculations were conducted for the reach and effectiveness outcomes using the Steppedwedge command in Stata Version 14. Although between 7 and 9 sites will participate, power calculations were estimated conservatively, assuming only 6 facilities (clusters) with 2 randomized into each of the 3 steps of the predominately open cohort (i.e., different patients at different timepoints) complete design. Calculations assume a two-tailed alpha of 0.05. VISN 19 leadership reports that few patients are currently being transitioned from MH to PC. Transition rates are <1% of patients in facilities who do not receive the FLOW intervention and between 1-16% of patients in facilities who do receive the FLOW intervention. Given an average of 1000 patients per quarter per facility based upon the Clinic Practice Manager data for VISN 19, a sample size of 6 clusters (24,000 patients in total) achieves 80% power to detect a difference in transition rates from 1% at baseline to 1.65% upon receiving FLOW. Power is >99% to detect a two-fold increase in patients who transition from SMH to PC. Reach, effectiveness, and most maintenance outcomes are binary variables at the patient level (e.g., whether one was transitioned to PC). These outcomes represent an open cohort trial, as different patients will be included at each timepoint within a given site. Adoption outcomes are both binary (e.g., whether a provider engaged in the FLOW process for at least 3 patients) and continuous (e.g., % of patients engaged in FLOW for each provider) at the provider level. These outcomes represent a closed cohort trial, as the same providers will be included at each timepoint. Adequate effectiveness will be declared if at least 90% of transitioned patients successfully transition without return to SMH in the 1 year follow-up period. Given a very conservative estimation that 4% of SMH patients transition from SMH to PC, an average of 40 patients per quarter per facility (4% of 1000 = 40), a sample size of 6 clusters (960 transitions in total) will allow for 80% power to detect a difference in the percentage of patients who successfully transitioned to primary care from 76.50% to 90% upon receiving FLOW.

Downstream effectiveness, or impact upon access, will be measured as increase in appointments within 7 days of requested date from pre-implementation to post-implementation. Data extracted from the Clinic Practice Manager suggests a fairly high baseline rate of clinic patients receive appointments within 7 days of desired date in VISN 19 (~75 to 80%). Given an average of 1000 patients per quarter per facility, a sample size of 6 clusters (24,000 patients in total) achieves 80% power to detect a difference in the percentage of patients receiving appointments within 7 days of desired date from 80% at baseline to 83% upon receiving FLOW. Power calculations are consistent with ICC values of .10, .15, .20, and .25 and would be similar to what is described above for the maintenance phase.

**Quantitative data analysis.** We will begin by describing the number of participants, providers, and sites (clusters) who were randomly assigned to each sequence and the numbers included at each quarter. Intervention conditions will initially be compared using generalized linear mixed models (HGLMs) for binary outcomes and hierarchical linear mixed models for continuous outcomes. Each model will include intervention (yes/no) and quarter as fixed predictors and models for reach, effectiveness (except for gain in provider hours), and maintenance will also include the value of the outcome during the baseline quarter as a fixed predictor. Site will be included in all models as a random effect. As we expect the intervention effect may be delayed and reach its peak at the end of the implementation period or that the effect may plateau or even decay during the maintenance period, we will also conduct a set of models where the treatment by time interaction is included as a fixed effect. Furthermore, given the sequences have different lengths of maintenance we will be able to examine whether maintenance varies with time since removal of external facilitator.

**Qualitative analysis.** We will examine associations between the proposed implementation factors (e.g., staffing levels, leadership support) and outcomes. To do so, we will use a mixed-methods comparative case study approach, a method that has been used to examine determinants of successful implementation of evidence-based practices in integrated healthcare systems. In this method, patterns of similarities and differences in relationships between implementation factors and outcomes are examined qualitatively and quantitatively across sites. This method is particularly suited for understanding why program implementation fails and succeeds at sites and is an appropriate evaluation design choice when it is not feasible to randomize sites or to have a large enough number of participating sites to determine statistical associations. We will

follow the steps of QCA, including: 1) operationalize the metric of success (example: successful implementation of FLOW leading to high reach), 2) identify which sites are classified as high implementation success vs. low implementation success, 3) Identify key conditions theoretically affecting implementation success (e.g., our implementation determinants), 4) create a matrix of scores signifying whether each site was high or low on each determinant, 5) analyze which implementation determinants in the matrix appear to be associated with high implementation success, 6) use freely available software (e.g., fsQCA 2.0) to analyze all possible configurations of selected implementation determinants, and 7) examine the results and resolve contradictions (e.g., if a contradictory result is potentially explained by a third, unmeasured variable or by the combination of variables) and re-run analyses if necessary. QCA can appropriately handle mixed methods data because the potential implementation determinants included in the analyses can be quantitative data such as staffing ratios, or can be qualitative data, such as presence or absence of a theme arising from qualitative interviews at each site. Outcomes produced from QCA will be information regarding whether a particular implementation determinant or combination of implementation determinants can be used to successfully distinguish between sites with high implementation success vs. low implementation success. This method has successfully been used for small n implementation studies such as the currently proposed study.

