At the request of VISN 19 we will also provide a less intensive implementation approach to the remaining VISN 19 sites, not included in the 7-9 sites in this project. The other sites will receive a toolkit for implementing FLOW and optional monthly calls for support. This may provide supplemental data regarding whether the intensive implementation approach at the primary 7-9 sites is necessary, or how many sites receiving the scaled down approach are able to implement FLOW. Because the EMR template will be implemented at all VISN 19 facilities, we will obtain data on the number of patients transitioned to primary care throughout VISN 19, regardless of their participation in this program evaluation process. Exploratory, descriptive analyses will compare implementation of FLOW at the 7-9 primary sites to the less intensive implementation sites.

**Study Design Overview.** A cluster-randomized stepped wedge design will examine implementation of FLOW in VISN 19. We chose a stepped wedge (see Table 1) because VISN 19 requested that all participating sites receive the FLOW program, and this design allows balancing of practical considerations with statistical considerations and randomization. This design is also appropriate because we expect the intra-class correlations in sites to be large. We will use the new CONSORT extension for cluster-randomized stepped-wedge trials to report methodological considerations and outcomes. Sites will be matched on resources and staffing ratios and simultaneously randomized to the time in which they begin the intervention (i.e., step 1, 2, or 3) on the basis of matching. Implementation of the program will be examined in three phases. First, data will be collected about the frequency of patient transition during the baseline phase. Next, FLOW will be implemented for 1 year with external and internal facilitation, and program evaluation will be guided by RE-AIM (see Table 1). Finally, there will be a minimum of a 1-year maintenance phase during which only data collection will occur.

**Sites.** Seven to nine VAMCs and very large CBOCs (>10,000 unique patients) from VISN 19 will participate, depending upon final leadership commitment at that time. VISN 19 is the geographically largest in the nation.

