**Table 1. Project timeline.**

Months	Year 1				Year 2				Year 3			
	Q1	Q2	Q3	Q4	Q1	Q2	Q3	Q4	Q1	Q2	Q3	Q4
Startup	X											
Cohort 1 (2 sites)		Implementation				Maintenance						
Cohort 2 (3 sites)			Implementation				Maintenance					
Cohort 3 (2 sites)				Implementation				Maintenance				
Assessment timepoints	●	●	●	●	●	●	●	●	●	●	●	●
Data analysis, papers										X	X	X
Report to VISN leaders	X	X	X	X	X	X	X	X	X	X	X	X

**Pre-implementation data-collection.** Before implementation (i.e., Q1, Q2, or Q3), baseline rates of patient transition from SMH to PC will be examined. Some sites currently have an EMR note template for discharge or transition out of specialty mental health; others document this as needed in medication management session EMR notes. We will use VA administrative databases to identify the pre-FLOW discharge rate. We will also collect assessments of implementation factors tapping the five CFIR domains: intervention

characteristics, outer setting, inner setting, characteristics of individuals, and process.

**Implementation of FLOW.** Implementation of FLOW will occur by implementation facilitation, an evidence-based strategy to change clinical practice, guided by the VA-based implementation facilitation manual. Facilitators partner with key stakeholders to plan change strategies, adapt them to the local context, and address barriers to implementation. Implementation facilitation is a flexible strategy that has been used effectively to create change in VA mental health services. Our multifaceted implementation strategy will use both external facilitation provided by [name], who has received training in facilitation from [name], and internal facilitation provided by a local champion at each site.

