As in the pilot, each site will receive FLOW materials and internal and external facilitation, in partnership with a local champion. The process starts with meetings with clinic leadership and identification of a local champion, typically a SMH provider. Sites will be given a list of ideal Internal Facilitator (IF) characteristics (e.g., strong communicator, opinion leader, prior QI or PE experience, well-established in their current position) and will nominate a provider who fits these. Next, the FLOW implementation team meets with providers from the affected clinics: SMH, PCMHI, and PC, to explain the rationale and procedures and answer any questions or concerns. With the input of providers and the local champion, local processes are identified to support communication between different clinics about patients transitioning. Sites are given access to the online FLOW report identifying patients who meet criteria for transition, provider and patient materials to explain the process of transition, and an EMR template with a progress note title to document the transition. The project team initially holds weekly meetings with the local champion to troubleshoot implementation, and implementation is flexibly differentiated to meet each site's identified barriers (see Table 4 for information about strategies employed by facilitators). Data will feed back to the internal facilitator on a monthly basis, including information about both the process of implementation and implementation success. Process data will include barriers and facilitators, types of actions or interventions the IF enacted to overcome barriers or leverage facilitators, assistance from the FLOW team, and local climate and context information arising that affects implementation. Implementation success metrics include the number of patients eligible and transitioned, which providers are engaging in FLOW and which providers have yet to transition any patients, etc. The internal facilitator is responsible for local implementation activities guided by regular calls with the FLOW team.

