**Table 2. RE-AIM outcomes measured during implementation and maintenance phases (Specific Aim 1).**

RE-AIM Domain	Project Outcome	Measured by:	Level of Analysis	Timepoint
Reach	Patient transition to PC, before and after FLOW implementation	Administrative data for EMR template	Patient	Baseline; quarterly
Effectiveness	Successful patient transition to PC, defined as PCP renews psychotropic prescriptions and patient does not return to SMH within 1 year	VA administrative data for FLOW EMR template use	Patient	Baseline; quarterly in impl. phase
	Patient satisfaction with FLOW	Qual. interviews	Patient	Post-transition
	Provider satisfaction with FLOW	Qual. interviews	Provider	Post-implementation
	Impact on access, measured as (1) gain in provider hours available and (2) gain in % of	CDW Completed Appointments	Provider	Baseline; quarterly

	patients who receive appointments within 7 days of desired date	Cube		
Adoption	Providers who use FLOW for >2 patients Providers' average % of patients engaged If turnover exists, new provider use of FLOW	VA administrative data for FLOW EMR template use	Provider	Quarterly in impl. phase
Implementation	Fidelity in implementation of FLOW components	Implementation checklist	Facility	Monthly
Maintenance	Sustainment, including all RE-AI metrics Continuing facilitation activities taken over by the local facility	All metrics above Assessment of IF behavior	Patient & provider	Quarterly during maintenance phase

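### Reach is tied to FLOW's own note template while the pre-FLOW rate comes from other records; if capture changes as each site starts FLOW, reach is biased in a direction and by an amount the plan does not fix

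*Combined protocol and SAP*

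**What the plan says.** The Implementation phase data collection paragraph gives the source for reach: "Use of the FLOW EMR template, extracted from administrative databases, will provide information on reach (% of patients transitioned pre vs. post FLOW implementation". In Table 2 the reach row, with baseline and quarterly timepoints, names "Administrative data for EMR template". The success row also lists a baseline timepoint and names "VA administrative data for FLOW EMR template use"; success there means "PCP renews psychotropic prescriptions and patient does not return to SMH within 1 year".

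The Implementation of FLOW text lists, among the materials handed to each site, "an EMR template with a progress note title to document the transition".

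The Pre-implementation data-collection paragraph names a different source: "We will use VA administrative databases to identify the pre-FLOW discharge rate". It describes documentation at that stage as uneven: "Some sites currently have an EMR note template for discharge or transition out of specialty mental health; others document this as needed", in notes of medication visits.

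The Methods text on the VISN's remaining sites adds a wider rollout, without a date: "Because the EMR template will be implemented at all VISN 19 facilities".

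Background and Significance defines a transition in concept: a planned discharge in which prescribing and monitoring pass to the primary care provider. No section turns this into an extraction rule for all periods.

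**The concern.** In a stepped wedge, the outcome must be ascertained in the same way before and after crossover. Here the recording tool arrives with the intervention. The share of real transitions that reach the count may therefore change just when a site starts FLOW, and the direction is open:

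- **Upward**, if control-period transitions written only in session notes are missed.
- **Downward**, if the pre-FLOW discharge count includes exits that are not planned transfers to primary care, or if transitions made after crossover without the template are missed.

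The model in Quantitative data analysis has intervention, quarter, the baseline-quarter outcome and a random site effect. A shift in capture timed to each site's crossover has the same pattern as the intervention indicator, so no other term can take it up.

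The same count feeds two more results: the control-period denominator of the success outcome, and the expected gain in provider time, which multiplies the number discharged by yearly appointment minutes. Seven-day access and completed new-patient appointments do not use the count and are not affected.

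**Working it through.** **Inputs.** From Power analysis: 6 sites, 2 per step, 3 steps (so 4 periods), 1000 patients per site-quarter, two-sided alpha 0.05, 1% versus 1.65%. The ICC of 0.10 is the lowest the plan lists. The documents give no capture fractions; every one below is an assumption.

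**Formula (Hussey-Hughes).** Let I = 6 and T = 4, let s² be the total variance, τ² = ICC × s² and v = (1 − ICC) × s² / 1000. Then

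Var = I·v·(v + T·τ²) / [(I·U − W)·v + (U² + I·T·U − T·W − I·V)·τ²].

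The layout gives U = 12, W = 56 and V = 28. The two brackets are therefore 72 − 56 = 16 and 144 + 288 − 224 − 168 = 40.

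**The plan's own figure.** With control-rate variance, s² = 0.01 × 0.99 = 0.0099, τ² = 0.00099 and v = 0.00000891. The standard error is 0.00231, z = 0.0065 / 0.00231 = 2.81, and power is Φ(2.81 − 1.96) = 80.3%. The same method gives 99.1% for 1% versus 2%. These match the stated 80% and >99%. If the variance is instead averaged over the two rates, s² = (0.0099 + 0.01623) / 2 = 0.01306 and power is 69%. Both bases are shown where power is compared.

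**No true effect, capture rising to 100% at crossover** (averaged variance; the range comes from applying the ICC to total or to within-site variance):

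| True rate | Control capture | Observed rates | Trials significant |
|---|---|---|---|
| 1% | 80% | 0.80% vs 1.00% | 14-15% |
| 1% | 61% | 0.61% vs 1.00% | 43-47% |
| 0.5% | 80% | 0.40% vs 0.50% | 9-10% |
| 0.5% | 61% | 0.305% vs 0.50% | 24-26% |

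For the first row with total variance, z = 0.0020 / 0.00219 = 0.91, and Φ(0.91 − 1.96) + Φ(−0.91 − 1.96) is about 0.15. The 0.5% rows are included because the plan puts the rate without FLOW below 1%. The 61% value is 1/1.65, the capture ratio that would by itself mimic the plan's detectable ratio.

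**True change from 1% to 1.65%:**

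| Measurement error | Observed rates | Power, control-rate variance | Power, averaged variance |
|---|---|---|---|
| None | 1.00% vs 1.65% | 80% | 69% |
| 80% capture after crossover | 1.00% vs 1.32% | 28% | 25% |
| Control over-count, 1.3-fold | 1.30% vs 1.65% | 27% | 24% |

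**Timing of the change.** In simulation with site and quarter effects, no true effect and a 1% rate, control capture of 80% or 61% gave false significance in about 14% or 43% of trials when capture changed at crossover. When it changed at all sites on one calendar date, the figures were 5.4% and 5.6%. A common calendar shift is a function of quarter alone, so the quarter terms take it up.

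**Larger effect.** At a true 1% to 4%, power stays above 99%. The 3-point difference is read as 4 − 0.8 = 3.2 (control capture 80%), 4 − 1.3 = 2.7 (1.3-fold over-count) or 3.2 − 1 = 2.2 (80% capture after crossover).

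**The case against.** The two source statements can be read as complementary: one sits under pre-implementation collection, the other under the implementation phase, and template use is itself drawn from administrative databases. The authors saw the uneven local documentation and named a baseline source that is not limited to a template. That reading is fair, but it confirms that the two periods are counted differently. It also does not fit the wording that takes reach before and after FLOW from the FLOW template.

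A VISN-wide rollout could remove most of the problem. This stands, on two conditions: one go-live date, and real use at every site before facilitation starts. The plan states neither.

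The plan calls 4% reach very conservative, so 1.65% is a detectable difference and not the expected one. This stands and limits the consequence. However, the plan's own range with FLOW starts at 1%, so small effects cannot be ruled out.

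A session-note mention may not meet the plan's definition of a transition, so omitting it is not always under-capture. Monthly feedback on providers and the fidelity checklist would also reveal some unrecorded transitions after crossover. Both points hold in part. They are reasons to write the definition into the extraction rule.

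A reader might infer that reach must rise by construction. That follows only if the FLOW template is also the control-period source and is not in use before crossover. The baseline paragraph points to other records, and the Table 2 reach row does not say FLOW, so local templates may count.

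**Conclusion.** The concern holds as a gap in ascertainment that should be fixed before data extraction. As written, the plan allows transitions to be counted differently by condition, and its model cannot separate a capture change at crossover from a FLOW effect. Neither the direction nor the size of any bias is established: both depend on an unstated go-live date and on capture fractions that the documents do not give.

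Near the powered difference of 0.65 points, moderate changes in capture matter in either direction. At the plan's 4%, the test is safe and the estimate moves by between −0.8 and +0.2 points in the cases shown. The fall from 80% to 28% should not be compared with results on another variance basis; the averaged-variance equivalent is 69% to 25%. The illustration follows the 4-period power design, not the 12 quarters of Table 1. The documents do not support a claim that a positive reach result would be an artefact, or that the access outcomes are compromised.

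**What to change.** Reconcile the four places: the Methods text on the VISN-wide template, Pre-implementation data-collection, Table 2, and Implementation phase data collection. Then:

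1. Define a transition by one extraction rule that matches the definition in Background and Significance and does not require the FLOW template. Existing local discharge templates and equivalent documented discharges should count.
2. Apply it identically in every control, implementation and maintenance site-quarter. Use the same count for reach, the success denominator and the provider-time gain.
3. Record each site's template go-live date, and keep FLOW-template counts as an adoption or process measure.
4. Free text and template notes may still be captured unequally under one rule. Pre-specify a sensitivity analysis of reach from structured prescription, consult and appointment data, with a fixed look-ahead. Do not use that definition as the success denominator, because prescription renewal by primary care and non-return are already part of that outcome.

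**Cost.** The query must be revised, possibly to cover all specialty mental health patients, and session-note discharges need a note search or chart sample. Some misclassification will remain. The sensitivity definition has lower power: at an assumed 90% sensitivity and 99% specificity in both conditions, the observed rates are 0.9 × 1% + 0.01 × 99% = 1.89% and 0.9 × 1.65% + 0.01 × 98.35% = 2.47%, and power is about 45%. A null result there would therefore say little, and it should not be the main definition. The 1% baseline in the power statement may need restating.

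### The 80% power for transition success counts 40 transitions in every pre-FLOW site-quarter; the plan's own rate allows at most 10, which puts 6-site power at about 49-55%

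*Combined protocol and SAP*

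**What the plan says.** All of this is in Section C, Power analysis, unless noted.

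- **Size of the design.** "Although between 7 and 9 sites will participate, power calculations were estimated conservatively, assuming only 6 facilities (clusters"), with two sites starting FLOW at each of three steps.
- **Patients.** "Given an average of 1000 patients per quarter per facility based upon the Clinic Practice Manager data for VISN 19", giving 24,000 in total.
- **Transition rates.** "Transition rates are <1% of patients in facilities who do not receive the FLOW intervention". The range that the plan gives for sites using FLOW is "between 1-16% of patients in facilities who do receive the FLOW intervention". The power calculation for reach uses 1% at baseline.
- **Transition success.** "Given a very conservative estimation that 4% of SMH patients transition from SMH to PC", which the plan turns into "an average of 40 patients per quarter per facility (4% of 1000 = 40"). It concludes that "a sample size of 6 clusters (960 transitions in total) will allow for 80% power" for 76.5% against 90%.
- **Separate adequacy rule.** "Adequate effectiveness will be declared if at least 90% of transitioned patients successfully transition" without return within one year.

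Table 1 and the paragraph on pre-implementation data collection give the three cohorts one, two and three quarters before FLOW. Table 2 lists transition success at baseline and quarterly during implementation. The Quantitative data analysis section models it with intervention and quarter as fixed effects and site as random. The end of the power discussion names ICCs of .10, .15, .20 and .25.

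**The concern.** Transition success can be observed only in patients who transition. Before FLOW, by the plan's own account, almost nobody does. The success calculation nevertheless gives pre-FLOW quarters the same number of transitions as FLOW quarters, while the reach calculation in the same paragraph uses a baseline rate one quarter as large (1% against 4%).

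The pre-FLOW transitions are the whole comparator for the 76.5%, so they limit the precision of the contrast. If their number is overstated fourfold, the 80% is overstated too. A non-significant comparison in the 6-site design could then be read as evidence of no difference when power was only about one half.

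**Working it through.** **1. Where 960 comes from.** 24,000 = 6 x 4 x 1000, so the calculation covers 4 quarters and 24 site-quarters. 960 = 6 x 4 x 40, so each of the 24 is given 40 transitions.

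**2. How many site-quarters are pre-FLOW.** Two sites each have 1, 2 or 3 pre-FLOW quarters: 2 x (1 + 2 + 3) = 12. The other 12 are FLOW.

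**3. Counts that follow from the plan's rates.**

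| | Plan | From the plan's rates |
|---|---|---|
| Pre-FLOW, per site-quarter | 40 | at most 1% x 1000 = 10 |
| Pre-FLOW, total | 12 x 40 = 480 | at most 12 x 10 = 120 |
| FLOW, total | 12 x 40 = 480 | 12 x 40 = 480 |
| All | 960 | about 600 |

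**4. Reproducing the stated 80%.** The model has a random site intercept, fixed quarter effects and a two-sided normal test at .05. The variance is p0(1 - p0) = .765 x .235 = .1798 in every cell, with the ICC as a share of total variance. For equal cells of size m:

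- s2 = .1798(1 - ICC)/m and t2 = .1798 x ICC
- I = 6 sites, T = 4 quarters, U = 12 FLOW cells
- W = 0 + 4 + 16 + 36 = 56 (squared quarter totals) and V = 2(9 + 4 + 1) = 28 (squared site totals)
- Var = I s2 (s2 + T t2) / [(IU - W) s2 + (U² + ITU - TW - IV) t2]

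At ICC .10 and m = 40, s2 = .004045 and t2 = .01798. The bracketed coefficients are 72 - 56 = 16 and 144 + 288 - 224 - 168 = 40. Then Var = .002352 and SE = .0485, so .135/.0485 = 2.784 and power = Φ(2.784 - 1.960) = 79.5%. At ICC .15 it is 81.3%. The same convention gives 80.3% for the plan's reach figure (1% to 1.65%) at ICC .10.

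**5. The same calculation with 10 pre-FLOW and 40 FLOW.** Cells are now unequal, so the variance comes from the matrix (generalised least squares) form of the same model. At ICC .10 the SE rises to .0701, so .135/.0701 = 1.925 and power = Φ(1.925 - 1.960) = 48.6%.

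| ICC | 40/40 | 10/40 |
|---|---|---|
| .10 | 79.5% | 48.6% |
| .15 | 81.3% | 50.3% |
| .20 | 83.3% | 52.5% |
| .25 | 85.5% | 54.9% |

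**6. Sensitivity (6 sites, 4 quarters).** The second column covers six conventions: variance at the pre-FLOW rate, at the mean rate, or specific to each cell, each with the ICC as a share of total variance or with p(1 - p) taken as the within-site variance.

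| Pre-FLOW/FLOW per site-quarter | Reproducing convention | All six |
|---|---|---|
| 10/40 | 49-55% | 44-66% |
| 10/70 (total stays 960) | 56-63% | 51-74% |
| 10/160 (16% every quarter) | 64-72% | 60-82% |
| 5/40 | 33-38% | not tabulated |

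A logistic simulation (1000 runs per setting, latent ICC .10 and .25, site and period effects, likelihood-ratio test) gives 86% at 40/40 and 53-58% at 10/40.

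**7. What 80% would need.** With FLOW at 40, 80% power needs 30-41 pre-FLOW transitions per site-quarter (17-53 across conventions). With 10/40, the pre-FLOW success rate detectable against 90% is 68.5-70.5% (67-73.5% across conventions), not 76.5%.

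**8. More sites or quarters, at 10/40, reproducing convention.** Seven quarters runs to the end of the last cohort's implementation year in Table 1 and assumes a constant effect.

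| Sites | 4 quarters | 7 quarters |
|---|---|---|
| 6 | 49-55% | 56-63% |
| 7 (2/3/2) | 53-60% | 60-68% |
| 9 (3/3/3) | 65-72% | 73-80% |

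**The case against.** **The 40 may be an average over all cells.** The plan does call it an average. Keeping 960 with 10 pre-FLOW then means 70 per FLOW site-quarter, and power is 56-63% (51-74% across conventions). This changes the number but does not restore 80%.

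**The 4% is deliberately low.** At the plan's upper rate of 16% in every FLOW quarter, power is still 64-72% on the reproducing convention. One of the six conventions reaches 80%, at ICC .20-.25, but it gives about 91-93% for the plan's own inputs at those ICCs and so is not the convention behind the stated 80%.

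**The convention is inferred.** This stands. The plan does not state it. It matches the success figure at ICC .10-.15 and the reach figure at .10, but gives 90-94% for the access figure (80% against 83%), where the plan states 80%. The safest statement is that power is well below 80%, with 49-55% as the best single range. Every convention loses about 27-34 points against its own 40/40 result.

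**The rates may not be quarterly.** This also stands. Section A reports the pilot's 16% as a share of unique patients over the implementation period, which reads as cumulative. If, as an assumption, both rates were annual (2.5 and 10 per quarter), power would be about 15-23%. That makes the problem worse.

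**The planned model also adjusts for the baseline-quarter outcome.** Neither the formula nor the simulation includes that covariate, and the direction of its effect is unknown.

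**Six sites is a low scenario, and the 90% rule does not use this comparison.** Both are true and limit the consequence. However, Table 1 shows 7 sites, and 7 sites still fall short.

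**Conclusion.** The concern holds: the power statement is wrong as written. The plan's own rate and patient numbers allow at most 120 pre-FLOW transitions, not 480. For the stated 6-site, 4-quarter design, power for 76.5% against 90% is then about 49-55% on the convention that reproduces the plan's 80%, and 44-66% across the conventions tried.

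This rests on three assumptions: the under-1% and 4% rates apply per quarter, as the plan uses them; FLOW site-quarters supply 40 transitions; and the treatment effect is constant. The 10 is a ceiling, while the 40 could be higher.

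The effect is limited to this one comparison. With 9 sites over 7 quarters the shortfall is modest or absent (73-80%, or 76-89% with both rates in the variance). It should be fixed, but it does not call the design into question.

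**What to change.** - Rerun the success calculation with separate counts per site-quarter: at most 10 pre-FLOW, 40 FLOW. If the software used accepts only equal cell sizes, use the unequal-cell form of the same model or a simulation.
- Replace the total of 960 with about 600, of which at most 120 are pre-FLOW, and state the per-cell assumption behind it.
- Restate either the 6-site power (expect about 49-55%) or the difference detectable with 80% power (expect about 68.5-70.5% against 90%), using the team's own rerun.
- State the ICC, the variance convention and the period to which the under-1% and 4% rates refer.
- Show 7 and 9 sites beside the 6-site case, over 4 and 7 quarters.

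The cost is one rerun and a few sentences in the Power analysis. No extra sites are needed, and design, analysis and data collection do not change. The downside is a less favourable power figure for 6 sites.
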